8.3.8 Management of Adverse Events (Including AESI)

Standard medical care will be provided at the study site for all AEs occurring during the study in accordance with the institutional guidelines. The severity of AEs will be graded per NCI-CTCAE (Version 5.0). The reason for study intervention withdrawal and the nature, duration, and results of any follow-up observations should be recorded in the appropriate section of the eCRF.

The study intervention may be interrupted at any time at the Investigator's discretion; however, the Medical Monitor must be notified. Re-initiation of study intervention may occur at the discretion of the Investigator with consideration of the following:

Clinical signs and symptoms	Proposed actions
CCI	
Severe Infections Grade ≥ 3	 If severe infection (CTCAE Grade ≥ 3), study intervention should be withheld until recovery. Signs and symptoms should be managed in accordance with the institutional guidelines. Re-initiation of the study intervention should be discussed with Medical responsible Permanently discontinue study intervention if severe infection is CTCAE Grade ≥ 4.

Asymptomatic Abnormal Laboratory Values	Proposed Actions
Neutrophil count: <1,000/mm³ [Grade ≥ 3]	Temporarily withhold the study intervention.
Platelet count: <50,000/mm³ [Grade ≥ 3]	 Clinical evaluation per institutional guidelines. Repeat the test, preferably within 72 hours but no later
Lymphocyte count: <500/mm³ [Grade ≥ 3]	than 7 days.
Transaminase elevation i.e., ALT and /or AST > 3xULN (if Baseline is normal) or > 3 × Baseline (if Baseline is abnormal) [Grade ≥ 2]	Withhold offending concomitant medication, if appropriate. Determine alternative contributing factors
Isolated elevation of Total Bilirubin i.e., > 2 × ULN (unaccompanied by transaminase elevation)	 If retest confirms the Grade ≥ 3 toxicity and alternative etiology [confounding factors such as concurrent medications or disease, disease flare or other risk
eGFR < 40 mL/min/1.73m²	factors] is not confirmed, permanently discontinue the
The eGFR is calculated by the Modification of Diet in Renal Disease equation: eGFR = 175 × (serum creatinine in mg/dL) ^{-1.154} × (age in years) ^{-0.203} × 0.742 (if female) × 1.212 (if race is black).	 study intervention. Monitor until resolution or return to Baseline, non-clinically significant level. Study intervention may be re-initiated if retest value

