LS means for change from Baseline in each score together with its 95% CIs will be presented by study intervention group and analysis visit, in a tabular and graphical form. The difference in the LS means between each study intervention group and placebo together with accompanying two-sided 95% CI will also be tabulated.

Empirical cumulative distribution function (eCDF) for Week 24 change from Baseline will be displayed by study intervention group to depict the treatment effect across the population.

[figure not shown]
14.3.14 Change from Baseline in FACIT-Fatigue Score at Week 24

[figure not shown]
Attributes of the estimand are described in the table below.

[figure not shown]
Endpoint	Change from Baseline in FACIT-Fatigue score at Week 24		
Population(s)	Participants with a baseline FACIT-Fatigue score and at least one post-baseline FACIT-Fatigue score in: Cohort A Cohort B		
Treatment	Enpatoran vs placebo		
Population-level summary measure	Model LS mean difference between study intervention groups		

The same analysis as described for change from Baseline in Skindex-29+3 scores (see section 14.3.13) will be conducted (same outputs will be provided).

[figure not shown]

[figure not shown]

[figure not shown]

[figure not shown]
Version 4.0

15 Safety Analyses

Safety analyses will be performed according to the as-treated principle on the safety analysis set by cohort and study intervention group unless otherwise specified. These will be conducted at final analyses of Cohort A and Cohort B. The analyses planned for the primary analysis of Cohort A are identified with an asterisk (*).

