- AST $\geq 3 \times ULN$, AST $\geq 5 \times ULN$, AST $\geq 10 \times ULN$, AST $\geq 20 \times ULN$

- (ALT or AST) \geq 3×ULN, (ALT or AST) \geq 5×ULN, (ALT or AST) \geq 10×ULN, (ALT or AST) \geq 20×ULN
- TBILI > 2×ULN
- Concurrent ALT \geq 3×ULN and TBILI \geq 2×ULN (*)
- Concurrent AST $\geq 3 \times ULN$ and TBILI $\geq 2 \times ULN$ (*)
- Concurrent (ALT or AST) $\geq 3 \times ULN$ and TBILI $\geq 2 \times ULN$ (*)
- Concurrent (ALT or AST) $\geq 3 \times ULN$ and TBILI $\geq 2 \times ULN$ and ALP $\geq 2 \times ULN$ (*)
- Concurrent (ALT or AST) $\geq 3 \times ULN$ and TBILI $\geq 2 \times ULN$ and ALP $\leq 2 \times ULN$ or missing (*)

Concurrent measurements are those occurring on the same date.

Categories will be cumulative, i.e., a participant with an elevation of AST \geq 10×ULN will also appear in the categories \geq 5×ULN and \geq 3×ULN. Liver function elevation and possible Hy's Law cases will be summarized using frequency and percentage.

An evaluation of drug-induced serious hepatotoxicity (eDISH) plot will also be created, with different symbols for different study intervention groups, by graphically displaying two figures with log-scale transformed axes presented as:

- Peak serum ALT (/ULN) vs peak total bilirubin (/ULN) during the on-treatment period including reference lines at ALT = 3×ULN and total bilirubin = 2×ULN
- Peak serum AST (/ULN) vs peak total bilirubin (/ULN) during the on-treatment period including reference lines at AST = 3×ULN and total bilirubin = 2×ULN

In addition, a listing of all TBILI, ALT, AST and ALP values for participants with a post-baseline TBILI $\geq 2 \times \text{ULN}$, ALT $\geq 3 \times \text{ULN}$ or AST $\geq 3 \times \text{ULN}$ will be provided.

Analysis for Parameters with NCI-CTCAE Grade Available

The laboratory toxicities will be tabulated using descriptive statistics (number of participants and percentages) during the on-treatment period. Grade 0 is not defined per NCI-CTCAE but will be used in derivations for simplicity to indicate that evaluable measurements are available. Laboratory values within normal range but considered grade 1 according to NCI-CTCAE will not be graded 1 (Grade 0, instead).

- A summary table of laboratory parameters (excluding amylase) by NCI-CTCAE grade will include number and percentage of participants with at least one value of Grade ≥ 0, Grade ≥ 3, Grade ≥ 4 during the on-treatment period.

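### The possible Hy's law count requires both liver limits to be crossed on the same date, and the two outputs that would show a delayed bilirubin rise are not planned for the Cohort A primary analysis

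*SAP*

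**What the plan says.** SAP Section 15.3 (Liver function tests) tabulates ALT, AST and total bilirubin singly and then in five joint rows: ALT with bilirubin, AST with bilirubin, either enzyme with bilirubin, and that last pairing split into higher and lower (or missing) ALP. The limits are 3xULN for the enzymes and 2xULN for bilirubin. All five rows are headed as concurrent, and the definition is: "Concurrent measurements are those occurring on the same date". The SAP adds: "Liver function elevation and possible Hy's Law cases will be summarized using frequency and percentage". It gives no separate definition of a possible Hy's law case, and no other row pairs a transaminase with bilirubin, so that count rests on the five rows.

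Two further outputs follow in the same section:

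- **eDISH plots.** "An evaluation of drug-induced serious hepatotoxicity (eDISH) plot will also be created", with one figure for ALT and one for AST. The ALT figure shows "Peak serum ALT (/ULN) vs peak total bilirubin (/ULN) during the on-treatment period", with reference lines at 3xULN and 2xULN. The dates of the two peaks play no part.
- **Liver listing.** "In addition, a listing of all TBILI, ALT, AST and ALP values for participants with a post-baseline TBILI" at or above 2xULN, or ALT or AST at or above 3xULN. One crossing is enough for entry.

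On timing, SAP Section 15 states: "The analyses planned for the primary analysis of Cohort A are identified with an asterisk". The five same-date rows have the asterisk. The eDISH plots, the liver listing and the single-parameter ALT, AST and bilirubin rows do not.

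**The concern.** The SAP holds two timing rules for one safety question. The table needs a single date on which both limits are crossed; the plots accept the two peaks on any dates. A participant can therefore sit in the upper-right quadrant of the plot and be absent from the table.

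At the final analyses a reader has both views. At the Cohort A primary analysis the reader has only the narrower one. Protocol Appendix 2 has the Firewall Team review the Cohort A Week 16 data, so this is a planned look at unblinded results. A zero in the joint rows could be read there as no possible Hy's law case, when it means only that none occurred on a single date. For an oral drug in Phase 2, one such case would matter.

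**Working it through.** The plan gives no figure to reproduce. The check has two parts: which outputs exist at which analysis, and what each rule does with the same participant.

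**1. Outputs by analysis** (asterisk rule in SAP Section 15, applied to Section 15.3)

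| Output | Pairs enzyme and bilirubin in one participant? | Date rule | Cohort A primary | Final |
|---|---|---|---|---|
| Five joint rows | Yes | Same date | Yes | Yes |
| CTCAE shift table, baseline to worst grade | No, one parameter at a time | None | Yes | Yes |
| Single-parameter ALT, AST, bilirubin rows | No | None | No | Yes |
| eDISH plots | Yes | Any dates (peaks) | No | Yes |
| Liver listing | Yes, by inspection | Any dates | No | Yes |

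In the Cohort A primary column, the only output that pairs the two is the same-date set. Laboratory data at that analysis run to Week 16 (SAP Sections 6.4 and 9.1). The missing asterisks are unlikely to be a text-extraction loss: neighbouring items in 15.3 keep theirs, and the SAP modification history for version 3.0 records that this section was edited to specify the analyses for the Cohort A primary analysis.

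**2. Rules applied to assumed trajectories**

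- Same-date rule: some date d has (ALT or AST at d) >= 3 and bilirubin at d >= 2, in multiples of ULN.
- Peak rule (eDISH quadrant): max(ALT or AST) >= 3 and max(bilirubin) >= 2.
- Listing rule: any value with ALT or AST >= 3, or bilirubin >= 2.
- Illustrative lag rule (an assumption, not in the documents): bilirubin >= 2 between 0 and 30 days after ALT or AST >= 3.

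Values below are ALT / bilirubin in xULN. They are assumed, and days follow the chemistry visits in Protocol Table 1 except Day 62, which stands for a retest. Protocol Section 8.3.8 asks sites, after a transaminase rise above 3xULN, to "Repeat the test, preferably within 72 hours but no later" than 7 days.

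| Trajectory | Same-date | Peak | Listing | 30-day lag |
|---|---|---|---|---|
| Day 29: 6 / 2.4 | Counted | Counted | Shown | Counted |
| Day 29: 8 / 1.4; Day 57: 2.5 / 2.6 | **Not counted** | Counted, point (8, 2.6) | Shown | Counted (57 - 29 = 28 days) |
| Day 57: 6 / 1.2; retest Day 62: 2.7 / 3 | **Not counted** | Counted, point (6, 3) | Shown | Counted (62 - 57 = 5 days) |
| ALT only: peak 5, bilirubin at most 0.9 | Not counted | Not counted | Shown | Not counted |
| Bilirubin only: peak 2.3, ALT 1 throughout | Not counted | Not counted | Shown | Not counted |

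The same-date and peak rules differ only in the two delayed trajectories. On the retest example, all five joint rows return zero: on Day 57 bilirubin is 1.2 < 2, and on Day 62 ALT is 2.7 < 3 (AST is taken as below 3 on both dates).

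**3. Size.** Cohort A plans about 25 participants per arm, so one omitted participant is 1/25 = 4% of an arm. That is the arithmetic of one case, not an estimate of how likely it is.

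**The case against.** The strongest reply is that such a case is not lost. The final analyses show it twice, in the eDISH plots and in a listing of every liver value for anyone crossing one limit. A labelled same-date table beside a labelled peak plot is a pair of complementary views, and the Cohort A primary analysis was narrowed on purpose in SAP version 3.0. Protocol Section 9.4.2.2 promises hepatotoxicity plots and participant profiles without tying them to that analysis. All of this stands. What it leaves is a count that omits the case at every analysis, and one planned analysis at which no listed output compensates.

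A reader might infer more, in three ways the documents do not support:

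- **That a liver case would go unnoticed.** Protocol Section 8.3.8 triggers withholding, evaluation and retesting on a transaminase rise alone or an isolated bilirubin rise alone. TEAEs and SAEs are starred for the Cohort A primary analysis, with all available adverse event data used (SAP Section 9.1). These do not pair the two values, but they mean that awareness of a case does not hang on this table.
- **That this is the first unblinded look.** The IDMC meets once 8 participants have completed 12 weeks or discontinued, then every four months (SAP Section 6.1), and interim analyses may come earlier. Their outputs are in the interim plan at SAP Appendix 18.3, which is not shown, so whether it includes linked liver displays cannot be checked.
- **That the same-date rule often fails.** The rule does not need the peaks to coincide, only one date with both values over their limits, and retests add such dates. The documents contain no data on how often bilirubin lags.

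It is also fair that a replacement count should not create problems of its own. One that required ALT or AST to rise first would still disagree with the plots for bilirubin-first cases, and one without an ALP split would lose a distinction the SAP already makes.

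**Conclusion.** The point holds as a reporting gap. The possible Hy's law count omits any participant whose bilirubin first reaches 2xULN after ALT and AST have fallen below 3xULN, and this is so at every analysis. At the Cohort A primary analysis, no output listed in the SAP would link the two rises; at the final analyses, the eDISH plots and the listing would.

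This rests on two readings: that the five joint rows are the source of the Hy's law count, since nothing else pairs the parameters, and that an absent asterisk means the output is not produced at the Cohort A primary analysis, as SAP Section 15 states. The frequency of such cases is unknown. No efficacy result, estimand or error rate is touched, and the documents do not support a claim that patient safety monitoring fails. It is worth changing because the change is cheap and a misread zero on this question would be costly.

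**What to change.** In SAP Section 15.3:

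1. Add the asterisk to both eDISH plots and to the liver listing, so that they are produced at the Cohort A primary analysis.
2. Keep the five same-date rows as they are.
3. Add a starred supplementary row counting participants with peak ALT or AST >= 3xULN and peak bilirubin >= 2xULN at any time on treatment, in either order. This matches the union of the upper-right quadrants of the two plots. Split it by ALP as in the existing rows, and state which ALP value is used when the two peaks fall on different dates.
4. Optionally, add a sub-row for a pre-specified lag between the two crossings.

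The cost is SAP wording, one extra set of rows, and two already specified outputs run earlier; no new data are needed. The downside is that the on-treatment period runs to last contact (SAP Section 9.8), so an early ALT rise and an unrelated late bilirubin rise would be counted together. A few such participants may need individual review, which the starred listing makes possible and the lag sub-row helps to sort.

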15.4 Vital Signs

Vital sign summaries will include all vital sign assessments from the on-treatment period. All vital sign assessments will be listed, and those collected outside the on-treatment period will be flagged in the listing.

Time window will be applied to assessments of vital signs (see section 9.7).

The following vital sign parameters will be summarized using descriptive statistics (mean, SD, median, Q1, Q3, minimum, and maximum) for raw values and changes from baseline at each scheduled analysis visit:

- Body temperature (°C)
- Systolic and diastolic blood pressure (mmHg)
- Respiration rate (bpm)
- Pulse rate (beats/min)
- Weight (kg)

The maximum on-treatment changes of vital sign measurements from Baseline will be grouped as follows:

Baseline Value	Change from Baseline
----------------	----------------------

Body temperature increase	< 37 °C; 37 - < 38 °C; 38 - < 39 °C; 39 - < 40 °C; ≥ 40 °C	< 1 °C, 1 − < 2 °C, 2 − < 3 °C, ≥ 3 °C
Pulse rate increase from baseline	< 100 bpm; ≥ 100 bpm	≤ 20 bpm, > 20 – 40 bpm, > 40 bpm
Pulse rate decrease from baseline	< 100 bpm; ≥ 100 bpm	≤ 20 bpm, > 20 – 40 bpm, > 40 bpm
SBP increase from baseline	< 140 mmHg; ≥ 140 mmHg	≤ 20 mmHg, > 20 – 40 mmHg, > 40 mmHg
SBP decrease from baseline	< 140 mmHg; ≥ 140 mmHg,	≤ 20 mmHg, > 20 – 40 mmHg, > 40 mmHg
DBP increase from baseline	< 90 mmHg; ≥ 90 mmHg	≤ 20 mmHg, > 20 – 40 mmHg, > 40 mmHg
DBP decrease from baseline	< 90 mmHg; ≥ 90 mmHg,	≤ 20 mmHg, > 20 – 40 mmHg, > 40 mmHg
Respiration rate increase from baseline	< 20 bpm; ≥ 20 bpm	≤ 5 bpm, > 5 − 10 bpm, > 10 bpm
Respiration rate decrease from baseline	< 20 bpm; ≥ 20 bpm	≤ 5 bpm, > 5 – 10 bpm, > 10 bpm

SBP = Systolic Blood Pressure, DBP = Diastolic Blood Pressure.

For each participant, the worst on-treatment value (i.e., lowest and highest when applicable) will be calculated. For the definition of baseline values, see section 9.2. Missing values will define a separate category.

The following summaries will be prepared for vital sign parameters as grouped above:

• Maximal shifts from baseline (changes in categories)

A participant data listing will present data for all vital signs. Worst on-treatment values (highest and/or lowest values depending on vital sign), and changes from Baseline in the highest categories as defined in the table above will be identified.

15.5 ECG Evaluations

ECG summaries will include all ECG assessments collected at Baseline and during the on-treatment period (Week 8, Week 20, Week 24 and ET). All ECG assessments will be listed, and those collected outside the on-treatment period will be flagged in the listing.

The time windows below will be applied to allocate measurements to analysis visits. Unscheduled ECG measurements will be used for the analysis.

Analysis Visit	Target Day	Window Range
Day 1	1	1
Week 8 Day 57	57	> 1 – 70
Week 20 Day 141	141	71 – 154
Week 24 Day 169	169	≥ 155

The following analyses will be performed for each applicable ECG parameter (RR, PR, QRS, QT, ventricular rate -denoted as HR in what follows-, and QTcF) by cohort and study intervention group:

- Descriptive statistics at Baseline, at each post-baseline time point and changes from baseline at each post-baseline time point
- Frequency (number and percentage) of participants with notable ECG values according to the following categories by analysis visit and during the on-treatment period. (*)
 - \circ HR < 50 bpm, < 40 bpm, < 30 bpm
 - o HR increase from baseline > 20 bpm, > 30 bpm, > 40 bpm
 - o HR decrease from baseline > 20 bpm, > 30 bpm, > 40 bpm
 - \circ PR > 200 ms and > 220 ms
 - o PR increase from baseline > 30 ms
 - \circ QRS > 110 ms
 - \circ QTcF > 450 ms, > 480 ms, > 500 ms
 - With/without concomitant antimalarial (ATC code level 3 = P01B)
 - o QTcF increase from baseline > 30 ms, > 60 ms
 - With/without concomitant antimalarial (ATC code level 3 = P01B)

ECG interpretation (normal, abnormal/not clinically significant, abnormal/clinically significant) will be summarized at Baseline and during the on-treatment period.

A shift table from baseline to the worst on-treatment observation in ECG interpretation (normal, abnormal/not clinically significant, abnormal/clinically significant, missing and total) will also be provided.

Complete ECG profiles will be provided for participants with at least one notable ECG value or one notable ECG increase as defined above. For these participants, all ECG parameter values collected during the study will be provided.

15.6 Columbia-Suicide Severity Rating Scale

The Columbia-Suicide Severity Rating Scale (C-SSRS) assesses the suicidal behavior and suicidal ideation in participants. Abnormal findings identified via the C-SSRS will be recorded as AE.

Time window will be applied to assessments of C-SSRS (see section 9.7).

Occurrence of suicidal behavior is defined as having answered "yes" to a least 1 of the 4 suicidal behavior subcategories (actual attempt, interrupted attempt, aborted attempt, preparatory acts or behavior).

Occurrence of suicidal ideation is defined as having answered "yes" to at least 1 of the suicidal ideation sub-categories (wish to be dead, non-specific active suicidal thoughts, active suicidal ideation with any methods [not plan] without intent to act, active suicidal ideation with some intent to act [without specific plan], and active suicidal ideation with specific plan and intent).

Occurrence of suicidality is defined as having at least 1 occurrence of suicidal ideation or at least 1 occurrence of suicidal behavior.

The number and percentage of participants with occurrence of suicidal behavior, occurrence of suicidal ideation and occurrence of suicidality will be summarized at Screening, Baseline and during the ontreatment period. Individual participant data listings will be also provided.

16 Analyses of Other Endpoints/Estimands

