7.1.2 Permanent Discontinuation

In rare instances, it may be necessary for a participant to permanently discontinue (definitive discontinuation) study intervention. If study intervention is definitively discontinued, the participant is encouraged to remain in the study until last safety follow-up (i.e., Week 26). The participant should complete the ET assessments as soon as possible and revert to the same study schedule (Table 1) based on the participant's Day 1 until the Safety follow-up visits are completed (see Section 1.3).

The participant must be withdrawn from study intervention in the event of any of the following:

- Enrollment despite violation of an exclusion criterion which, in the Investigator's, and/or Sponsor's opinion, makes discontinuation of the participant necessary.
- Participation in any other interventional study during the duration of this study for which the Investigator considers discontinuation of the study intervention necessary.
- Occurrence of pregnancy.
- Occurrence of a clinical condition (e.g., SAE, SFI defined severe flare) for which discontinuation is considered necessary by the Investigator and/or the Sponsor/designee.

- Non-compliance to study visits, study intervention etc., judged as significant by the Investigator or Sponsor, e.g., taking CCI of the study intervention doses.
- An unplanned event that necessitates discontinuation of study intervention for more than 4 weeks.
- If a participant is unblinded.

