Appendix 8 Efficacy and Patient-Reported Outcome Assessments and Procedures

Refer to Table 1 for the study population and frequency for each assessment and procedure.

Columbia-Suicide Severity Rating Scale (C-SSRS)

Patients with SLE, especially those with neuropsychiatric manifestations, are at higher risk for suicide than expected. In a review of the medical records of 300 SLE patients over a 20-year period, 2% had a documented history of attempted suicide; one of them was fatal. All patients had a history of depression at the time of the suicide attempt (Karassa 2003).

The C-SSRS (Posner 2007) assesses the suicidal behavior and suicidal ideation in participants. Occurrence of suicidal behavior after randomization is defined as having answered "yes" to at least 1 of the 4 suicidal behavior subcategories (actual attempt, interrupted attempt, aborted attempt, and preparatory acts, or behavior). Occurrence of suicidal ideation after randomization is defined as having answered "yes" to at least 1 of the suicidal ideation sub- categories (wish to be dead, nonspecific active suicidal thoughts, active suicidal ideation with any methods [not plan] without intent to act, active suicidal ideation with some intent to act [without specific plan], and active suicidal ideation with specific plan and intent).

Rationale

The C-SSRS is a low burden, tool designed to track suicidal AEs throughout any intervention study and is considered to be the "gold standard" for assessment. This scale is administered by the clinician or trained designee during the Screening Visit. The measure succinctly covers the full spectrum of suicidality addressing both behavior and ideation and is now strongly recommended by the US Food and Drug Administration in clinical studies. It is the prospective version of the Columbia-suicide classification system commissioned by the Food and Drug Administration, which provided the data for their safety analyses, and is used across numerous industry and National Institutes of Mental Health-sponsored studies.

Assessments

The C-SSRS is a unique and simple method of assessing both behavior and ideation that tracks all suicidal events and provides a summary of suicidality. It assesses the lethality of attempts and other features of ideation (frequency, duration, controllability, reasons for ideation and deterrents), all of which are significantly predictive of completed suicide.

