9.7 Time Window

Unless otherwise specified, study measurements will be assigned an analysis visit based on their actual assessment date as described in the table below.

Analysis Visit	Target Day	Window Range
Day 1	1	1
Week 2 Day 15	15	> 1 – 21
Week 4 Day 29	29	22 – 42
Week 8 Day 57	57	43 – 70
Week 12 Day 85	85	71 – 98
Week 16 Day 113	113	99 – 126
Week 20 Day 141	141	127 – 154
Week 24 Day 169	169	155 – 176
Safety Follow-up Visit Week 26 Day 183	183	≥ 177

For the Cohort B final analysis, the following table will be used:

Analysis Visit	Target Day	eCRF visit	Window Range
Day 1	1	Any	1
Week 2 Day 15	15	Any	> 1 – 21
Week 4 Day 29	29	Any	22 – 42
Week 8 Day 57	57	Any	43 – 70
Week 12 Day 85	85	Any	71 – 98
Week 16 Day 113	113	Any	99 – 126
Week 20 Day 141	141	Any	127 – 154
Week 24 Day 169	169	Any	155 – 176
		Any apart from Safety Follow-up visit	177 – 182
Safety Follow-up Visit Week 26 Day 183	183	Safety Follow-up visit	177 – 182
		Any	> 182

In case multiple assessments are assigned to the same window, the closest value to the target day will be considered for analysis. If two values are observed with the same distance to the target day (one before and one after), then the earlier value will be used for analysis.

In case several time points are scheduled on a same day, specifications will be provided for the related parameters. For parameters not expected to be collected at each visit, visit windows will be combined. As an example, if a parameter is not measured at Week 2, the Week 4 visit window will extend from > 1 to 42.

CONFIDENTIAL

INFORMATION

Definition of On-treatment Period 9.8

The on-treatment period is defined as the time from the first dose of study intervention to the date of last contact.

9.9 **Exposure time**

Duration of exposure to study intervention = end date – date of first dose of study intervention +1, where:

• end date is the date of last dose of study intervention.

9.10 **Imputation of Missing Data**

Disease history:

Incomplete dates for documented diagnosis of CLE or SLE will be imputed as follows:

- If the day is missing, it will be imputed to the 1st day of the month.
- If both day and month are missing and the year is available, the month and day will be imputed as January 1st.
- If the date is completely missing, no imputation will be performed.

Exposure:

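### SAP 15.6 puts the C-SSRS through one-record-per-window selection although its only post-baseline summary is any occurrence, so the table may undercount suicidality

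*SAP*

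**What the plan says.** SAP 15.6 sends the instrument to the general windowing section: "Time window will be applied to assessments of C-SSRS (see section 9.7". That section (SAP 9.7) assigns each assessment to an analysis visit and then selects: "In case multiple assessments are assigned to the same window, the closest value to the target day will be considered for analysis". Two values equally far from the target are resolved in favour of the earlier. For instruments not collected at every visit, "For parameters not expected to be collected at each visit, visit windows will be combined". The C-SSRS is not scheduled at Week 2, so its Week 4 window runs from after Day 1 to Day 42.

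The outcome in 15.6 is of the ever/never kind: "Occurrence of suicidality is defined as having at least 1 occurrence of suicidal ideation or at least 1 occurrence of suicidal behavior". Participants with behavior, ideation and suicidality "will be summarized at Screening, Baseline and during the ontreatment period". No post-baseline table by visit is planned. SAP 9.8 sets the period: "The on-treatment period is defined as the time from the first dose of study intervention to the date of last contact".

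On the protocol side, the Schedule of Activities has a C-SSRS at ET as well as at Weeks 4, 8, 12, 16, 20, 24 and 26. Section 7.1.2 says of a participant who stops study drug but stays in the study: "The participant should complete the ET assessments as soon as possible and revert to the same study schedule (Table 1". Appendix 8 defines the outcome by answers on the instrument: "Occurrence of suicidal behavior after randomization is defined as having answered" yes to at least one of the four behavior subcategories, with a parallel definition for ideation.

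**The concern.** Choosing the record nearest a target day suits a by-visit mean, where one value per participant per visit is wanted. It does not suit an ever/never count, where one positive answer decides the participant's status and every record in the period matters. Since 15.6 plans no post-baseline display by visit, the selection step has no useful role there. It can only remove records from the count.

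The design also produces the situation in which it would do so. A participant who stops drug has an ET C-SSRS and then returns to the scheduled visits. Both records lie inside the on-treatment period, and they may fall in the same window. Unscheduled assessments raise the same problem. At stake is whether the table that compares arms on suicidality counts every participant with a positive answer.

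**Working it through.** **The rule applied to single cases.** The Week 16 window is Days 99 to 126, target Day 113.

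- Positive ET on Day 105, negative Week 16 on Day 113: distances 8 and 0. Day 113 is kept and the positive is not counted. The retained record is the later one.
- Negative Week 16 on Day 113, positive ET on Day 120 at study withdrawal: distances 0 and 7. Day 113 is kept again. The retained record is the earlier one.

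**One 28-day window.** Inputs: Week 8 window Days 43 to 70, target Day 57 (SAP 9.7); scheduled visit within ±3 days of target (protocol Schedule of Activities); one extra C-SSRS on any other day of the window. The extra record is kept only if it is nearer the target than the scheduled one, or equally near and earlier.

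| Scheduled on Day | Extra record kept if on Days | Days kept | Days discarded (27 minus kept) |
|---|---|---|---|
| 54 | 55–59 | 5 | 22 |
| 55 | 56–58 | 3 | 24 |
| 56 | 57 | 1 | 26 |
| 57 | none | 0 | 27 |
| 58 | 56–57 | 2 | 25 |
| 59 | 55–58 | 4 | 23 |
| 60 | 54–59 | 6 | 21 |

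The extra record is therefore discarded on 21 to 27 of the window's 28 days (21/28 = 75%; 27/28 = 96%). The scheduled visit's own day is included in the 28.

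**All on-treatment C-SSRS windows.** Week 4 (Days 2 to 42) has 41 days, Weeks 8, 12, 16 and 20 have 28 each, and Week 24 (Days 155 to 176) has 22. The total is 41 + 4 × 28 + 22 = 175 days. Removing the six scheduled days leaves 169 possible days for an extra record.

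- Scheduled visits on target: 169 of 169 discarded. The retained record is later in 27 + 4 × 14 + 14 = 97 cases and earlier in 169 − 97 = 72.
- Scheduled visits 3 days early: 169 − 6 × 5 = 139 discarded (82%).
- Scheduled visits 3 days late: 169 − 6 × 6 = 133 discarded (79%).

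For the Cohort B final analysis, Week 24 also takes Days 177 to 182 from visits other than safety follow-up. Those days are 8 to 13 days from target, so they would only add discarded days.

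**After the fix.** If every on-treatment record counts towards occurrence, none of the 169 days is lost.

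**What these figures are not.** They are loss fractions given that two C-SSRS records share a window. The documents give no rate for such collisions and no rate of positive answers.

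**The case against.** The best counter-argument is that the authors meant to use every record. The general specifications in SAP Section 9 link windowing to descriptive statistics by visit, and say that unscheduled visits also enter worst post-baseline values. An ever/never count is in substance a worst-value summary. SAP 15.3 carries the same windowing sentence for laboratory data and still reports worst on-treatment grades, so the sentence may be standard text not intended to restrict such summaries. The wording in 15.6 about at least one occurrence during the on-treatment period also reads naturally as any yes in that span.

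This makes the intention plausible, but it does not settle the text. Laboratory data have explicit worst-on-treatment wording. Vital signs (15.4) are said to use all on-treatment assessments. The ECG section (15.5) names ET and brings in unscheduled records. Section 15.6 has none of these, and ET is a visit in the protocol schedule, so a sentence about unscheduled visits does not clearly cover it. A programmer following 15.6 would have grounds to apply the selection rule.

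A second objection stands in large part: the event is not lost from the report. Section 15.6 provides C-SSRS listings and says abnormal findings are recorded as adverse events, and protocol 8.2.6 points the same way. The cover is incomplete, because protocol Appendix 8 names only behavior items and ideation questions 4 or 5 for adverse event reporting. The milder ideation items count as occurrence in 15.6 but might have no adverse event record.

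A reader might infer that a safety signal would be hidden, or that 75% to 96% of ET assessments would be lost. The documents support neither. The listings and adverse event tables remain, and the percentages require a same-window collision and an ET day spread evenly over the window. Nor do they show that the ET record is the one most likely to be positive. Under protocol 8.2.6 discontinuation is considered after signs appear and risk is assessed, so the triggering answer may be on the preceding scheduled C-SSRS.

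**Conclusion.** The point holds as a defect in the stated rule for one descriptive safety table. Taken literally, SAP 15.6 with 9.7 can drop a true positive from an any-occurrence count, and the ET procedure makes two records in one window possible by design. The retained negative may be earlier or later than the positive.

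Given a collision in a 28-day window and a scheduled visit within ±3 days of target, the extra record is discarded on 21 to 27 of 28 days. How many participants this would affect is unknown. As a hypothetical scale, one uncounted participant in a Cohort A arm of about 25 would move that arm's rate by 1/25 = 4 percentage points.

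The effect is confined to the between-arm summary. The table carries no inference, is not among the listed secondary safety endpoints, and is not marked for the Cohort A primary analysis. A reader might also want suicidal-behavior adverse events or suicide deaths counted as C-SSRS behavior. That does not follow from the windowing problem, and it would depart from the protocol's instrument-based definition in Appendix 8.

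**What to change.** Replace the windowing sentence in SAP 15.6 with a statement that all post-baseline C-SSRS assessments in the on-treatment period (scheduled, unscheduled and ET) count towards the occurrence of suicidal ideation, suicidal behavior and suicidality, and that the closest-value rule of 9.7 applies only to any display by visit. Leave the definition of occurrence based on C-SSRS answers, as in the protocol.

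The cost is one SAP sentence and the matching programming specification. It needs no new data and touches no efficacy analysis. If the authors already meant to use all records, the edit simply puts that in writing.
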